8.7 Stopping Rules

We will monitor the study subjects for both efficacy and toxicity. We will allow continuous accrual on to the study unless a stopping rule is met or the target accrual is reached. The study may also be stopped based on the recommendation of the investigators, the TCI DSMC, or at Incyte's discretion for any reason.

Steroid-refractory GVHD:

We expect itacitinib monotherapy to be safe because of its extensive use in >700 patients prior to this trial. However, in order to protect study subjects we have designed three stopping rules that will terminate the trial early if itacitinib monotherapy as a treatment for GVHD is either too toxic or ineffective. First, our preliminary data show that the incidence of steroid-refractory GVHD using the definition in section 2.3 in the low risk population eligible for this trial is 38%. For an itacitinib monotherapy trial to be successful, the proportion of patients who develop steroid-refractory GVHD should not exceed 38%. We expect that patients who do not respond to itacitinib will be responsive to steroid treatment and we will continuously monitor the incidence of steroid-refractory GVHD in all study subjects. Patients will be considered to have steroid refractory GVHD if their GVHD is treated with systemic steroids and they either do not respond by day 28 of steroid treatment. The trial will be halted if the incidence of steroid-refractory GVHD is greater than the

associated boundary value b_k listed in the table below, among the k patients enrolled in the trial, then accrual will be halted.

Maximum # of Patients, k	5	6-8	9-10	11-13	14-16	17-19	20-22	23-25	26-28	29-31	32-35
Boundary, b _k	3	4	5	6	7	8	9	10	11	12	13
Maximum # of Patients, k	36-38	39-41	42-44	45-48	49-51	52-54	55-58	59-61	62-65	66-68	69-70
Boundary, b _k	14	15	16	17	18	19	20	21	22	23	24

Specifically, if more than 3 out of the first 5 patients, 4 out of the first 8 patients, 5 out of the first 10 patients, 6 out of the first 13 patients, or 24 out of the first 70 patients, experience steroid-refractory GVHD, the trial will be halted for safety considerations.

The operating characteristics of this stopping rule are as follows:

	True Steroid Refractory Rate 24% 30% 33% 0.38 40% 42%						
Probability of Early Stopping	0.10	0.36	0.54	0.83	0.88	0.94	

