Using these boundaries, if the true steroid refractory rate is 24%, 30%, 33%, 38%, 40% or 42%, the probability of stopping the trial early is 0.10, 0.36, 0.54, 0.83, 0.88, and 0.94 respectively.

Serious infections:

Itacitinib monotherapy has been shown to be safe in over 700 patients. However, its use as a therapy for acute GVHD is investigational. The primary toxicity of treatment for GVHD is infection. Our preliminary data show that the incidence of serious infections in the first 90 days of systemic steroid treatment for GVHD is 59%. Therefore, if the proportion of study patients who experience serious infections exceeds 59%, we would not further study itacitinib monotherapy for GVHD treatment. If the incidence of serious infections is greater than the associated boundary value bk listed in the table below among the k patients enrolled in the trial, then accrual will be ended.

Maximum # of Patients, k	6	7	8-9	10-11	12-14	15-16	17-18	19-20	21-22	23-24
Boundary, b _k	4	5	6	7	8	9	10	11	12	13
Maximum # of Patients, k	25-27	28-29	30-31	32-34	35-36	37-38	39-41	42-43	44-45	46-48
Boundary, b _k	14	15	16	17	18	19	20	21	22	23
Maximum # of Patients, k	49-50	51-52	53-55	56-57	58-60	61-62	63-65	66-67	68-70	
Boundary, b _k	24	25	26	27	28	29	30	31	32	

Specifically, if more than 4 out of the first 6 patients, 5 out of the first 9 patients, 10 out of the first 20 patients, 14 out of the first 31 patients, or 29 out of the first 70 patients, experience serious infections within 3 months, the trial will be halted for safety considerations.

The operating characteristics of this stopping rule are as follows:

	True Serious Infections Rate 35% 41% 45% 50% 55% 60%					
Probability of Early Stopping	0.10 0.31 0.55 0.79 0.96 0					

Using these boundaries, if the true serious infections rate is 30%, 33%, 40%, 45%, 50% or 60%, the probability of stopping the trial early is 0.10, 0.18, 0.57, 0.83, 0.96, and 1 respectively.

Non-relapse mortality:

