In this low risk patient population the the six-month non-relapse mortality rate is 9%. If, in the unlikely event that itacitinib-related toxicities increased the risk for non-relapse mortality we would want to terminate the trial early. We will continuously monitor the rate of non-relapse mortality. The trial will be halted if there is sufficient evidence that the six month NRM rate is higher than 9%. Specifically, if the incidence of non-relapse deaths within 6 months of study administration is greater than the associated boundary value b_k listed in the table below, among the k patients enrolled in the trial, then accrual will be halted for safety considerations.

Maximum # of Patients, k	11	12-26	27-45	46-65	66-70
Boundary, b _k	1	2	3	4	5

Specifically, if more than 1 out of the first 11 patients, 2 out of the first 26 patients, 3 out of the first 45 patients, 4 out of the first 65 patients, or 5 out of the first 70 patients, experience NRM within 6 months of study administration, the trial will be halted for safety considerations.

The operating characteristics of this stopping rule are as follows:

	True NRM Rate					
	3%	6%	8%	9%	11%	
Probability of Early Stopping	0.10	0.45	0.68	0.77	0.89	

Using these boundaries, if the true NRM rate is 3%, 6%, 8%, 9%, or 11%, the probability of stopping the trial early is 0.10, 0.45, 0.68, 0.77, and 0.89 respectively.

All the stopping rules were computed using the toxbdry function in R and calculations of this function are based on methods described in Chapter 12 of Jennison and Turnbull and in the illustrative paper by Ivanova, Qaquish and Schell^{46,47}.

An enrollment rule to prevent an excessive number of toxicities as described in Song and Ivanova will be used to inform us of the number of additional patients we can recruit when the current patient has not yet completed follow-up⁴⁸ Formally, the trial can enroll *m* new patients such that $r + x + m \le b_{n+m} + M$, $r + x + m - 1 < b_{n+m-1} + M$, and $n + m \le K$ where *r* is defined as the number of patients that have not completed follow-up and are still being followed for toxicity; *x* is the number of patients that have experienced toxicity, *n* is the total number of patients enrolled to date and *M* is the fixed design parameter. To be able to complete this low-risk study in a timely manner, we allow *M* to be 30.

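### Section 8.7 gives two different infection stopping rules, the refractory-GVHD benchmark is 38% in one place and 33% in another, and the wording about excess risk does not describe the protective boundaries

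*Combined protocol and SAP*

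**What the plan says.** Section 8.7 sets three continuously monitored rules. Each halts the trial when the event count among the first k patients is greater than a tabulated b_k.

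- **Serious infections.** The stated standard is "if the proportion of study patients who experience serious infections exceeds 59%, we would not further study itacitinib monotherapy for GVHD treatment". The table gives b = 6 at k = 9, 11 at k = 20, 16 at k = 31 and 32 at k = 70, with a stopping probability of 0.10 at a 35% true rate. The prose below it gives limits of 5/9, 10/20 and 14/31, ending "or 29 out of the first 70 patients, experience serious infections within 3 months", and it states "if the true serious infections rate is 30%, 33%, 40%, 45%, 50% or 60%, the probability of stopping the trial early is 0.10" at the first of those rates and 0.57 at 40%.
- **Steroid-refractory GVHD.** Section 8.7 says "the proportion of patients who develop steroid-refractory GVHD should not exceed 38"%, and the synopsis also uses 38%. Section 11.2 gives the historical rate as 33%. The table ends at 24/70. The printed stopping probabilities run over 24%, 30%, 33%, "38%, 40% or 42%, the probability of stopping the trial early is 0.10, 0.36, 0.54, 0.83, 0.88, and 0.94".
- **NRM.** The aim is that "in the unlikely event that itacitinib-related toxicities increased the risk for non-relapse mortality we would want to terminate the trial early", and the trigger is "The trial will be halted if there is sufficient evidence that the six month NRM rate is higher than 9"%. The limits are 1/11, 2/26, 3/45, 4/65 and 5/70. The plan states that if "the true NRM rate is 3%, 6%, 8%, 9%, or 11%, the probability of stopping the trial early is 0.10, 0.45, 0.68, 0.77" and, at 11%, 0.89.

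The synopsis (refractory GVHD and NRM) and section 11.2 (all three outcomes) summarise the rules as early termination when the rate goes above its historical value.

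**The concern.** A monitoring board needs one boundary per outcome and one account of what a crossing means. For infections it has two boundary sets in the same subsection. For refractory GVHD the boundary is single, but the historical rate that explains it has two values. For NRM the table and prose agree on the counts, but the sentence introducing them promises evidence that mortality is above 9%, while the operating characteristics show that a drug with exactly 9% NRM would usually be halted.

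Two things are at stake. Some infection counts would halt accrual under one half of the subsection and not under the other. And a halt could be reported as excess harm when the boundary does not establish that.

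**Working it through.** **Method.** Let f_k(x) be the probability that the trial is still running after k patients with x events, at true rate p. Then f_k(x) = (1 − p)·f_{k−1}(x) + p·f_{k−1}(x − 1) for x ≤ b_k, and any x > b_k is a halt. P(halt) = 1 − Σ f_70(x). Outcomes are taken as known at once. Inputs are the b_k tables in section 8.7. Looking from patient 1 or from the first tabulated k gives the same P(halt), because b_k is taken as constant up to that k.

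**Reproducing the printed figures**

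| Rule | True rates | Printed | Recomputed |
|---|---|---|---|
| NRM | 3, 6, 8, 9, 11% | 0.10, 0.45, 0.68, 0.77, 0.89 | 0.102, 0.451, 0.683, 0.773, 0.894 |
| Refractory | 24, 30, 33, 38, 40, 42% | 0.10, 0.36, 0.54, 0.83, 0.88, 0.94 | 0.100, 0.361, 0.548, 0.819, 0.890, 0.939 |
| Infection table | 35, 41, 45, 50, 55% | 0.10, 0.31, 0.55, 0.79, 0.96 | 0.100, 0.325, 0.554, 0.816, 0.955 |

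Only the infection value at 50% is off by more than two points.

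**1. Infection table against infection prose**

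| First k patients | Table halts at | Prose halts at | Counts that halt under the prose only |
|---|---|---|---|
| 9 | 7 | 6 | 6 |
| 20 | 12 | 11 | 11 |
| 31 | 17 | 15 | 15–16 |
| 70 | 33 | 30 | 30–32 |

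| True rate | 30% | 33% | 40% | 45% | 50% | 60% |
|---|---|---|---|---|---|---|
| Prose states | 0.10 | 0.18 | 0.57 | 0.83 | 0.96 | 1 |
| Table boundary gives | 0.03 | 0.06 | 0.28 | 0.55 | 0.82 | 0.99 |

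A boundary with a constant nominal level at every patient (an assumed method), tuned to stop with probability 0.10 at 30%, gives the prose limits 4/6, 5/9, 10/20, 14/31 and 29/70. It stops with probability 0.10, 0.19, 0.57, 0.83, 0.96 and 1.00 at the six rates. The prose therefore describes a second design, not a misprint of the table.

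**2. Refractory benchmark.** The tabulated boundary halts with probability 0.82 at 38% (printed 0.83) and 0.55 at 33% (printed 0.54). The lowest observed rate at which it can be crossed is 24/68 = 35.3%. That is below 38% but above 33%, so whether any crossing falls below the benchmark depends on which figure is meant.

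**3. Wording against boundary.** P(halt) when the true rate equals the benchmark is 0.77 (NRM, 9%), 0.82 (refractory, 38%) and 0.99 (infection table, 59%, a rate the plan does not print).

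The smallest crossing count late in the trial, with the one-sided exact tail P(X ≥ x) at the benchmark:

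- NRM 5/65 = 7.7% against 9%: 0.71
- Refractory 25/70 = 35.7% against 38%: 0.69
- Infection 33/70 = 47% against 59%: 0.98

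None of these indicates a rate above the benchmark.

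The largest count that finishes without a halt, with P(X ≤ x) at the benchmark:

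- NRM 5/70 against 9%: 0.39
- Refractory 24/70 against 38%: 0.31
- Infection 32/70 against 59%: 0.017

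**The case against.** Cautious safety boundaries are a legitimate choice in a low-risk population, and section 8.7 prints what they do: 0.77 at 9% and 0.83 at 38%. For NRM and refractory GVHD the table and prose agree, so nobody could misapply those two rules. The explicit demand for evidence of a higher rate appears only for NRM; the synopsis and section 11.2 are one-line summaries that point back to 8.7. Section 1.2 reports 33% serious infections in patients without GVHD or steroids, which gives an infection rule set near 30–35% a visible rationale. Most halts at the benchmark also have an observed rate above it (87% NRM, 82% refractory, 69% infection).

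Much of this stands. The boundaries need not change because of the wording, and the printed NRM and refractory probabilities are sound. But an observed rate above the benchmark is not evidence that the true rate is above it: the median one-sided p-value at such halts is 0.32, 0.30 and 0.46. The objection also does not touch the two infection rules or the 38%/33% conflict.

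A reader might go further in three ways that the documents do not support.

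- A crossing might be read as meaning that the rate has not been shown to be better than historical. That fails for NRM and refractory GVHD, where 5/70 and 24/70 finish unstopped without showing improvement.
- The clause in section 11.2 about improvement being unlikely might be read as defining a crossing. It is a separate power of the protocol committee to stop for futility, whereas 8.7 halts for safety.
- The 80–81% power might be read as an overall chance of success. The synopsis and section 11.2 already tie it to the response rate.

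**Conclusion.** The point holds in three parts.

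- **Infections.** Two incompatible stopping rules stand in one subsection. They differ by three events at 70 patients, and the stated 0.57 at 40% compares with 0.28 from the table. This is the most pressing part, because the rule cannot be applied as written.
- **Refractory GVHD.** The historical rate is 38% or 33%, and the halt probability at benchmark moves from 0.82 to 0.55 accordingly.
- **Wording.** The boundaries are protective. A crossing does not by itself show a rate above historical and, for NRM and refractory GVHD, finishing without a crossing does not show improvement.

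The halt probabilities assume that each outcome is known before the next patient is counted, an assumption under which the printed NRM and refractory figures are reproduced. The infection value at 59% uses the table boundary. The documents do not show which infection set or which refractory benchmark was intended.

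**What to change.** The sponsor should:

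1. Reconcile the infection table with its prose in section 8.7, so that one boundary set remains with operating characteristics computed from it, and add the stopping probability at 59%.
2. Reconcile 38% (synopsis, section 8.7) with 33% (section 11.2).
3. Reword the NRM trigger in section 8.7, and the matching summaries in the synopsis and section 11.2, to say that the boundaries are protective and that a crossing does not by itself show a rate above historical. The alternative is to recompute the boundaries so that they do what the wording says.

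The cost of the rewording route is a few sentences, one corrected infection paragraph and one exact calculation, with no threshold moved by the wording change. The downsides are that a halt will carry a weaker stated meaning and that one of the two infection boundary sets must be dropped. The alternative in item 3 is a redesign of the monitoring rules and would need new operating characteristics.

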9.0 DRUG INFORMATION

9.1 Itacitinib Adipate

- Commercial names for the drug: Itacitinib (INCB389110)
- Classification-type of agent: selective JAK1 inhibitor

- Description: Itacitinib may be formulated as 25 mg, 100 mg, 200 mg, or 300 mg (free base equivalent) SR tablets. These tablets contain the active ingredient, hypromellose, microcrystalline cellulose, lactose monohydrate, and magnesium stearate, and may be coated with a nonfunctional coating. Itacitinib also may be formulated as an IR tablet but this preparation will not be used in this trial.
- Mode of action:

Pharmacologic inhibition of JAK/STAT signaling has shown potential in the treatment of GVHD while maintaining the anti-leukemia effect of allogenic transplant^{49,50}. *In vivo* JAK/STAT-signaling inhibition with ruxolitinib improved survival of mice developing aGVHD and reduced histopathological GVHD grading, serum levels of proinflammatory cytokines, and expansion of alloreactive luc-transgenic T cells³¹. Additionally, ruxolitinib impaired differentiation of CD4+ T cells into IFN- γ and IL-17A–producing cells, both T-cell phenotypes linked to GVHD. Ruxolitinib also increased FoxP3+ regulatory T cells, which are linked to immunologic tolerance.

JAK1/2 inhibition with ruxolitinib has also shown clinical benefit in patients with acute GVHD and chronic graft-versus-host disease (cGVHD). In patients with steroid-refractory GVHD treated with ruxolitinib, the ORR was 84.3% (27/32; 10 CRs and 17 PRs) in acute GVHD and 80% (16/20) in cGVHD³³. The median time to response was less than 2 weeks. After additional follow-up (medians of 19 and 24 months for acute GVHD and cGVHD, respectively), 1-year overall survival rates of 62.4% (confidence interval [CI]: 49.4%-75.4%) and 92.7% (CI: 84.7%-100%) were reported for steroid-refractory acute GVHD and cGVHD, respectively. The median duration of ruxolitinib treatment was 5 months for patients with steroid-refractory aGVHD and 10 months for patients with steroid-refractory aCHD, reflecting the different biology of the diseases (Zeiser et al 2016).

Itacitinib, an inhibitor of JAK/STAT signaling with selectivity for JAK1, showed similar pharmacologic inhibition of interferon signaling, resulting in the decreased expression of CXCR3, reduced GVHD, and improved survival when administered for 30 days after allo-HSCT in mice (Investigator brochure). Preliminary data in subjects with acute GVHD who received itacitinib in combination with corticosteroids (prednisone or methylprednisolone; Study INCB 39110-108) indicate ORRs of 83.3% at Day 28 for subjects with first-line aGVHD and up to 66.7% for subjects with steroid-refractory aGVHD.

Pharmacokinetics:

Eight formulations of itacitinib (IR or SR) have been studied in multiple healthy volunteer studies. Sustained release is likely needed to maintain JAK inhibition over the dose administration interval given the relatively short half-life of IR formulation and to reduce the peak/trough ratio. Of the formulations studied, the SR3 formulation was selected for future study as other formulations had a larger food effect, lower relative bioavailability compared with the reference IR formulation (relative bioavailability = 48% for SR3), or more variable PK. Following a single dose of 300 mg itacitinib SR3 (3 × 100 mg tablets), there was a 46% increase in C_{max} but only a 17% increase in total exposure (AUC0- ∞) when administered with a medium-fat meal. The non-clinically significant impact on total exposure when administered with a medium-fat meal supported the administration of itacitinib SR3 without regard to food. Currently, the SR3 100 mg formulation is the only formulation being used in any study of subjects with underlying conditions. A preliminary analysis comparing single doses of 100 mg (1 × 100 mg SR3 tablet), 200 mg (2 × 100 mg SR3 tablet), and 300 mg (3 × 100 mg SR3 tablet; fasted) demonstrated that exposures increase in a greater-than-proportional manner.

Following multiple-dose administration of itacitinib SR3 400 BID or 800 QD with a medium fat meal, steady state was generally reached after 48 hours. Compared with Day 1, there was approximately 60% and 15% accumulation in AUC0-T for the 400 mg BID and 800 mg QD doses, respectively, following a medium-fat meal. The highest total daily exposure after multiple-dose administration was achieved after administration of 600 mg BID (29.0 μ M·h [calculated as 2 × AUC0-12]). Mean half-life of itacitinib is generally reported in the range of 3 to 9 hours with an overall mean of

approximately 5 hours. After itacitinib 400 mg BID and 800 mg QD administration with a mediumfat meal, the intersubject CV% ranged from 25% to 34% for C_{max} and 23% to 40% for AUC0-T. Pharmacokinetics of Itacitinib SR3 100 mg Tablet in Healthy Subjects After Single Dose Administration

Dose (mg)	Study INCB39110-	Ν	C _{max} (μM)	T _{max} (h)	AUC [♭] (µM.h)	C _{min} (μM)
200mg	105ª	36	0.343 ± 0.176	2.0 (0.5-4.0)	1.48 ± 0.572	NA
(fasting)						
300mg	105ª	23	0.668 ± 0.335	1.5 (0.5-4.0)	2.85 ± 1.45	NA
(fasting)						
300mg	102	23	0.587 ± 0.334	1.5 (0.5-4)	2.49 ± 0.928	NA
(fasting)						
300mg	102	12	0.875 ± 0.468	2.5 (1.5-6.0)	3.02 ± 1.35	NA
(medium fat						
meal)						
300mg (high	102	12	1.05 ± 0.465	4.0 (1.5-8.0)	3.59 ± 1.13	NA
fat meal)						

NA = not applicable.

PK parameters reported as mean ± SD except tmax, which is presented as median (range).

a Data (Study INCB 39110-105) are preliminary.

b AUC is AUC0–∞ for single-dose administration or AUC0-т for multiple-dose administration.

• Adverse reactions:

The underlying GVHD condition is a major contributor to morbidity in the post-transplant setting and should not be confused with adverse reactions attributable to investigational agents. Treatment-emergent adverse events (TEAE) are reported regardless of attribution to GVHD, steroids, other transplant related events, or study drug and full safety assessments must take attribution into account. As of the data cutoff, 29 subjects in Study INCB 39110-108 had received itacitinib in combination with corticosteroids, a pharmacologic class with its own significant toxicity (section 1.2). All 29 subjects had at least 1 TEAE, 28 of those (96.6%) were grade 3 or higher. The most frequently reported TEAEs were consistent with expectations for GVHD patients and included thrombocytopenia (41.4%), diarrhea (37.9%), abdominal pain (34.5%), and peripheral edema, fatigue, and hypokalemia (31.0% each). One subject with preexisting thrombocytopenia had a Grade 3 dose-limiting event of thrombocytopenia that was attributed to GVHD progression. Other frequently reported TEAEs (≥20%) included hyperglycemia (27.6%), decreased appetite, headache, hypophosphatemia, nausea, and tachycardia (24.1% each), and dry mouth, hypoalbuminemia, sepsis, and vomiting (20.7%), all common events in patients with GVHD treated with steroids. The most frequently reported TEAE leading to permanent discontinuation of itacitinib was GI hemorrhage (3 subjects; 10.3%), a known complication of GI GVHD. The only other TEAE leading to permanent discontinuation of itacitinib in more than 1 subject was thrombocytopenia (2 subjects; 6.9%). Eight subjects (27.6%) in the study had a fatal TEAE, six of which occurred after discontinuing study treatment. Three subjects experienced multi-organ failure (10.3%); two sepsis (6.9%); and one patient each developed GI hemorrhage, hematochezia, electrolyte imbalance, or acute respiratory distress syndrome (3.4% each). Of note, two of these patients discontinued the study drug due to a TEAE (electrolyte imbalance and multiorgan failure). None of these deaths were attributed to itacitinib.

Serious adverse events were reported in 22 subjects (75.9%) of which 7 (24.1%) were treatment related. The most frequently reported SAE was sepsis (6 subjects; 20.7%). Other SAEs reported in more than 1 subject included GI hemorrhage (4 subjects; 13.8%), multiorgan failure (3 subjects; 10.3%), diarrhea (3 subjects; 10.3%), and acute kidney injury (2 subjects; 6.9%). Treatment-related SAEs included sepsis (3 subjects; 10.3%) and klebsiella sepsis, pancytopenia, diarrhea, pneumatosis intestinalis, pneumoperitoneum, and CMV viremia (1 subject each; 3.4%). As of the data cutoff, 25 subjects (83.3%) had discontinued treatment: 11 subjects (36.7%) because of a TEAE, 4 subjects (13.3%) because of progressive disease, 4 subjects (13.3%) for reasons classified as 'Other.' The most frequently reported TEAE leading to permanent discontinuation of itacitinib was GI hemorrhage (3 subjects; 10.3%). The only other TEAE leading to permanent discontinuation of itacitinib in more than 1 subject was

thrombocytopenia (2 subjects; 6.9%). A preliminary, unaudited summary of the TEAEs in \geq 3 subjects from Study INCB 39110-108 is presented in the following table:

MedDRA Preferred Term	200 mg QD (n = 14)	300 mg QD (n = 15)	Total (N = 29)
Thrombocytopenia	2 (14.3)	10 (66.7)	12 (41.4)
Diarrhea	7 (50.0)	4 (26.7)	11 (37.9)
Abdominal pain	6 (42.9)	4 (26.7)	10 (34.5)
Edema peripheral	4 (28.6)	5 (33.3)	9 (31.0)
Fatigue	5 (35.7)	4 (26.7)	9 (31.0)
Hypokalemia	5 (35.7)	4 (26.7)	9 (31.0)
Hyperglycemia	5 (35.7)	3 (20.0)	8 (27.6)
Decreased appetite	3 (21.4)	4 (26.7)	7 (24.1)
Headache	5 (35.7)	2 (13.3)	7 (24.1)
Hypophosphatemia	4 (28.6)	3 (20.0)	7 (24.1)
Nausea	5 (35.7)	2 (13.3)	7 (24.1)
Tachycardia	5 (35.7)	2 (13.3)	7 (24.1)
Dry mouth	4 (28.6)	2 (13.3)	6 (20.7)
Hypoalbuminemia	4 (28.6)	2 (13.3)	6 (20.7)
Sepsis	3 (21.4)	3 (20.0)	6 (20.7)
Vomiting	5 (35.7)	1 (6.7)	6 (20.7)
Acute kidney injury	4 (28.6)	1 (6.7)	5 (17.2)
Anemia	3 (21.4)	2 (13.3)	5 (17.2)
Edema	3 (21.4)	2 (13.3)	5 (17.2)
	3 (21.4)	2 (13.3)	5 (17.2)
	3 (21.4)	2(13.3)	5 (17.2)
Hematochezia	3 (21.4)	2 (13.3)	5 (17.2)
Hypertension	1 (7.1) 5 (25.7)	4 (20.7)	5 (17.2)
	3(33.7)	0	5 (17.2)
Hypoganinagiobulinemia	3(21.4)	2 (13.3)	5 (17.2)
	2(14.3)	2 (13.3)	J(17.2)
increased	2 (14.3)	2 (13.3)	4 (13.0)
Asthenia	4 (28 6)	0	4 (13.8)
Blood creatinine increased	3 (21 4)	1 (6 7)	4 (13.8)
Cough	3 (21.4)	1 (6.7)	4 (13.8)
Cytomegalovirus infection	4 (28.6)	0	4 (13.8)
Neutrophil count decreased	2 (14.3)	2 (13.3)	4 (13.8)
Weight decreased	4 (28.6)	0	4 (13.8)
Abdominal distension	1 (7.1)	2 (13.3)	3 (10.3)
Arthralgia	0	3 (20.0)	3 (10.3)
BK virus infection	1 (7.1)	2 (13.3)	3 (10.3)
Blood bilirubin increased	3 (21.4)	0	3 (10.3)
Blood fibrinogen decreased	2 (14.3)	1 (6.7)	3 (10.3)
Confusional state	0	3 (20.0)	3 (10.3)
Constipation	1 (7.1)	2 (13.3)	3 (10.3)
Cytomegalovirus viremia	1 (7.1)	2 (13.3)	3 (10.3)
Dizziness	2 (14.3)	1 (6.7)	3 (10.3)
Dyspnea	2 (14.3)	1 (6.7)	3 (10.3)
Ecchymosis	1 (7.1)	2 (13.3)	3 (10.3)
Hematuria	2 (14.3)	1 (6.7)	3 (10.3)
Hyperbilirubinemia	2 (14.3)	1 (6.7)	3 (10.3)
Hyponatremia	2 (14.3)	1 (6.7)	3 (10.3)
Hypotension	3 (21.4)	0	3 (10.3)
Hypoxia	2 (14.3)	1 (6.7)	3 (10.3)
Malnutrition	3 (21.4)	0	3 (10.3)
Iviental status changes	3 (21.4)	U 0 (40 0)	3 (10.3)
Multiorgan failure	1 (7.1)	2 (13.3)	3 (10.3)
Pancytopenia	3 (21.4)	0	3 (10.3)
Pneumatosis intestinalis	2 (14.3)	1 (6.7)	3 (10.3)
	3 (21.4)	U 4 (0 7)	3 (10.3)
Syricope	2 (14.3)	1 (6.7)	3 (10.3)
White blood on the second	3 (21.4)	U 2 (20 0)	3 (10.3)
docropsod	U	3 (20.0)	3 (10.3)
ueuleaseu			1

Experience with itacitinib monotherapy in non-GVHD disease states suggests a favorable safety profile. The following TEAE data are based on all Incyte-sponsored clinical studies from the start of the itacitinib clinical development program through December 13, 2016. As of the data cutoff date, 777 subjects have been exposed to itacitinib as monotherapy (493 subjects; including 284 healthy volunteers and 209 subjects with underlying disease such as RA, chronic plaque psoriasis, or MF).

System Organ Class MedDRA Preferred Term	Overall Frequency (All Grades) N (%)	Grade 3 or Grade 4 N (%)	Frequency of Serious Events ^a N (%)	
Blood and lymphatic system d	isorders			
Anemia ^b	36 (17.2)	26 (12.4)	5 (2.4)	
Neutropenia ^c	8 (3.8)	3 (1.4)	-	
Thrombocytopeniad	31 (14.8)	19 (9.1)	-	
Gastrointestinal disorders				
Diarrhea	21 (10.0)	-	-	
Nausea	26 (12.4)	1 (0.5)	-	
Vomiting	15 (7.2)	1 (0.5)	-	
General disorders and adminis	stration site conditions			
Asthenia	6 (2.9)	2 (1.0)	-	
Fatigue	35 (16.7)	-	-	
Pyrexia	17 (8.1)	2 (1.0)	2 (1.0)	
Infections and infestations				
Herpes zoster	6 (2.9)	-	-	
Nasopharyngitis	12 (5.7)	-	-	
Oral candidiasis	2 (1.0)	-	-	
Sinusitis	9 (4.3)	-	-	
Upper respiratory tract infection	30 (14.4)	-	-	
Urinary tract infection	10 (4.8)	2 (1.0)	2 (1.0)	
Investigations				
Alanine aminotransferase increased	6 (2.9)	-	-	
Aspartate aminotransferase increased	7 (3.3)	-	-	
Nervous system disorders	•	•	•	
Dizziness	15 (7.2)	-	-	
Headache	18 (8.6)	2 (1.0)	-	

The following table presents expected TEAEs attributable to itacitinib monotherapy:

^aFor the purpose of expediting safety reporting in clinical trials, only serious adverse reactions that occurred for more than 1 subject will be considered expected.

ITACITINIB	MONTHEF	RAPY					
SUMMARY	OF SERIO	OUS NON-HEMATOL	OGIC AND	HEMATOL	OGIC ADVERSE	EFFECTS	WITH

DISEASE	PHASE	INTERVENTION	SERIOUS NON- HEME AE (>1%)	GRADE 3-4 HEME AE
Psoriasis	ll (n=50)	ITA dose escalation vs placebo	None	None reported
Myelofibrosis	ll (n=87)	3 ITA dose cohorts (100mg BID, 200mg BID, 600mg QD)	None	AE's decreased with higher doses suggesting heme effects were from myelofibrosis ↓Hb: 0 grade 4, 25-33% grade 3 ↓PLT: 3-6% grade 4, 12.5-44% grade 3 ↓ANC: 0-2.4% grade 4, 0-2.4% grade 3
All ITA monotherapy studies	Pooled data (n=777)	n/a	None	↓Hb: 12.4% ↓PLT: 9.1% ↓ANC: 1.4%

• Drug interactions:

Cytochrome P450 3A4 is the major isozyme responsible for the metabolism of itacitinib in human liver microsomes. In a cultured human hepatocyte assay, itacitinib did not induce CYP1A2, CYP2B6, or CYP3A4/5 activity or mRNA levels, suggesting that the potential to induce P450 in clinical studies is low. In vitro assays indicated that itacitinib is a substrate of P glycoprotein (P-gp) and breast cancer resistance protein (BCRP). In addition, the potential for itacitinib to cause clinical drug-drug interactions (DDIs) through CYP inhibition is low based on IC50 values and clinical doses based on the current Committee for Medicinal Products for Human Use guideline and draft FDA guidance^{51,52}. For efflux transporters, *in vitro* studies demonstrated that itacitinib is a substrate of P-gp and BCRP. In addition, itacitinib is not an inhibitor of BCRP but is a weak inhibitor of P-gp with an IC50 of 41.4 μ M. For uptake transporters, *in vitro* studies demonstrated that itacitinib is not a substrate of hepatic transporters OATP1B1/1B3, and inhibitory potentials toward hepatic transporters OATP1B1/1B3 and renal transporters OAT1/3 and OCT2 are low.

Because the primary metabolic pathway is metabolism by CYP3A4, a 1-way drug-drug interaction study (INCB 39110-110) was conducted to evaluate the impact of co-administration of itraconazole (a potent CYP3A4 inhibitor) or rifampin (a potent CYP3A4 inducer) on itacitinib exposure in healthy subjects. This was an open-label study to assess the effect of multiple doses of itraconazole or rifampin on the single-dose PK of itacitinib. Thirty-six healthy subjects were divided into 2 cohorts of 18 subjects.

In Cohort 1, subjects received each of the following treatments in succession, as shown below: Day 1: Itacitinib 200 mg SR (100 mg SR × 2) single dose administered orally in the fasted state.

Days 2 through 5: Itraconazole 200 mg QD in the fed state (4 doses).

Day 6: Itacitinib 200 mg SR (100 mg SR × 2) single dose and itraconazole 200 mg

single dose in the fasted state.

Day 7: Itraconazole 200 mg single dose in the fed state.

In Cohort 2, subjects received each of the following treatments in succession, as shown below: Day 1: Itacitinib 200 mg SR (100 mg SR \times 2) single dose administered orally in the fasted state. Days 2 through 8: Rifampin 600 mg QD in the fasted state (7 doses).

Day 9: Itacitinib 200 mg SR (100 mg SR \times 2) single dose and rifampin 600 mg single dose in the fasted state.

There was a notable change in exposure when itacitinib was coadministered with either a potent CYP3A4 inhibitor (~5-fold increase in exposure) or a potent CYP3A4 inducers (~80% decrease in exposure).

- Storage and stability: All itacitinib drug product should be stored at ambient conditions (15°C to 30°C, or 59°F to 86°F).
- Administration: Itacitinib tablets are to be administered orally.
- Availability: Provided by Incyte
- Any remaining/expired/used is to be destroyed on site according to the institution standard operating procedure for drug destruction and documented on the drug accountability logs.
- Drug Accountability:

The principal investigator, or a responsible party designated by the investigator, must maintain a careful record of the inventory and disposition of the investigational drug, itacitinib. The drug accountability records will capture drug receipt, drug dispensing, drug return and final disposition.

